1.7.2. Secondary Efficacy Endpoint

Assessment of improvement at each visit compared to baseline by the handling physician.

The following assessment methods will be applied (frontal clinical assessment or by images):

- FWCS - Fitzpatrick Wrinkle Classification Scale
- GAIS - Global Aesthetic Improvement Scale Assessment

Patients' Reported Outcomes (PROs):

- Subject Satisfaction Questionnaire

1.7.3. Primary Safety Variable

Evaluation of related adverse events up to the 3-months FU visit.

1.7.4. Secondary Safety Variable

- Evaluation of the pain and discomfort of the treatment as reported by the subject on a visual analog scale (VAS).
- Subject Subjective Downtime Assessment.

2 STUDY POPULATION

2.1. Inclusion Criteria

1. Male or female 35-70 years old diagnosed with clinically evident static periorbital wrinkles.
2. Willingness and ability to comply with all required study activities including returning for follow-up visits and protocol requirements.
3. The subject is able to provide written informed consent and perform the study's activities according to HIPAA guidelines and/or Israeli law, depending on each specific study site.
4. Fitzpatrick wrinkle score of 3-7 in the peri-orbital areas per the treating investigator and clinically noticeable wrinkles in the treating area.
5. Stable body weight during the study period.
6. Skin Type I – V as per Fitzpatrick Skin Scale.

2.2. Exclusion Criteria

1. Past treatment with Tixel device.
2. The subject may not undergo treatment by the Tixel device according to the device's contraindications for use, as defined in the User Manual and in the Instructions for Use and by any other labeling of the device.
3. Subjects who, in the investigator's opinion, have a history of poor cooperation, noncompliance with medical treatment, or unreliability.
4. Female subjects who are pregnant, or planning to become pregnant, or have given birth less than 3 months ago or are lactating.
5. Subjects with significant exposure to critical amounts of ultraviolet light (Sun-tan).
6. Subjects who have had the following treatments:
 - a. a cosmetic procedure to improve peri-orbital rhytides (i.e. periorbital or eyelid/eyebrow

- surgery, brow lift, CO2/Erbium/similar laser/fractional resurfacing, radiofrequency treatment) within 12 months
- b. prior facial treatments with laser, surgical, chemical or light-based facial treatments within the previous 12 months, over the periorbital area including botulinum toxin injections, microdermabrasion or prescription level glycolic acid treatments.
 - c. Injectable filler in cheeks (mid face) temples and in the upper face area to be treated within 12 months of investigation.
7. Any subject who have visible scars or other visible changes over the treated areas that may affect evaluation of response and/or quality of photography.
8. Subjects with any type of active cut, wound, inflammation, lesion (benign, premalignant or malignant) or active bacterial, viral, fungal, or herpetic infection on the skin on the designated treatment sites or in close proximity to it.
9. Existing or history of the following (when discussing skin conditions, refers only to the periorbital sites):
- a. skin malignancy, or any diagnosis of suspected malignancy
 - b. Collagen or vascular or bleeding disease
 - c. Immunosuppression or autoimmune disease
 - d. Erythema with or without blistering
 - e. History of post inflammatory hyperpigmentation.
 - f. Active Acne Vulgaris, HSV-1, or any existing skin condition/disease that in the investigator's opinion would interfere with the evaluation of the safety of the study treatment and evaluation.
 - g. Any skin pathology which can induce bullous lesions, urticaria, or demonstrate a Koebner phenomenon (psoriasis, lichen planus, etc.).
 - h. Any disease that inhibits pain sensation
 - i. History of keloid formation, or hypertrophic scarring
 - j. Conditions affecting healing rate (i.e. diabetes mellitus I or II, vascular condition, etc.)
 - k. neuromuscular disorders
10. Subjects who have used, within 30 days, any medication that can cause dermal hypersensitivity or affect skin characteristics over the treated area (i.e. topically applied Retinoids, Hydroquinone, Chemical peel of any strength: glycolic acid, lactic acid, salicylic

acid)

11. Subjects who have used, systemic treatment which may induce dyspigmentation, such as amiodarone, clofazimine, minocycline or chloroquine.
12. Subjects currently taking or have taken an oral retinoid in the past six months; Subjects currently taking long-term oral steroid treatment.
13. Concurrent therapy that, in the principal investigator's opinion, would interfere with the evaluation of the safety or efficacy of the study treatment.
14. Subjects who anticipate the need for major surgery or overnight hospitalization during the study that can affect the study schedule or treatment evaluation.
15. Enrollment in any active study involving the use of investigational devices or drugs.
16. Any other cause per the principal investigator's discretion.

Study visits procedures (see Table 2)

4 EVALUATION TOOLS

The following evaluation tools will be used in this study:

4.1. Fitzpatrick Skin Scale (FSS)

Assessment of subject's skin color will be determined prior to study procedure by the Investigator using the FSS. The scale delineates skin color into the categories as shown in Table 3- Fitzpatrick Skin Scale Evaluation. **שגיאה! מקור ההפנייה לא נמצא.** See

Table 3- Fitzpatrick Skin Scale Evaluation

Skin Type	Description
Type I	White skin that never tans and always burns easily
Type II	White skin that tans slightly and always burns easily
Type III	Light brown skin that tans gradually and can burn moderately
Type IV	Moderately brown skin that tans well and burns slightly
Type V	Dark brown skin that tans profusely and burns rarely
Type VI	Black skin with deep pigmentation that never burns

4.2. Fitzpatrick Wrinkle Classification Scale (FWCS)

Assessment of subject wrinkles will be performed by the Investigator and in addition, will be performed by three board-certified independent dermatologists or plastic surgeons ("Raters"), using the Fitzpatrick Wrinkle Classification Scale (FWCS) categories as shown in Table 4. The FWCS is a clinically validated assessment tool used to assess skin wrinkle severity and elastosis on a scale from 1 through 9, where the lower score is considered better.

The investigator will assess FWCS at baseline, 1-months and 3 months follow up visit, while the raters will assess only at baseline and 3 months follow up visit.

4.3. Blinded Identification of 3-Month Images

Assessment of each subject's baseline and 3-month follow-up images viewed simultaneously will be performed by the Independent Photographic Reviewers ("Raters") who will be blinded to the study subject's visit (baseline and 3-month follow-up visit). Each rater will view each subject's randomized baseline and 3-month follow-up images and assess which set of images represent the subject's post-treatment images. Each photograph will have a unique identification number, but the sets of images will not be arranged in any specific order. The Raters will assign a single FWCS score per subject at each time point. A subject will be considered a success if at least 2 out of the 3 Raters correctly identify the 3-month images and the FWCS score is ≥ 1 .

Table 4- Fitzpatrick Wrinkle and Elastosis Scale

Class	Description	Score	Description
I	Fine wrinkles	1-3	Mild: Fine texture changes with subtly accentuated skin lines.
II	Fine to moderate depth wrinkles, Moderate number of lines	4-6	Moderate: Distinct papular elastosis (individual papules with yellow translucency under direct lighting) and dyschromia
III	Fine to deep wrinkles, numerous lines, with or without redundant skin folds	7-9	Severe: Multipapular and confluent elastosis (thickened, yellow, and pallid) approaching or consistent with cutis rhomboidalis.

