1.7. Study Endpoints

1.7.1. Primary Efficacy Endpoint

Comparison of the proportion of subjects with a ≥ 1 -score improvement on the FWCS at the 3-month visit compared to baseline as determined by at least 2 out of 3 blinded Independent Photographic Reviewers.

The study design assumes a 65% success rate of subjects with a ≥ 1 -score change on the FWCS, therefore, greater or equal to 65% of subjects must be rated with a ≥ 1 -score improvement 3 months after treatment and must be statistically significantly.

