6.1. Determination of Sample Size

- The objective of this study is to demonstrate that study participants positively respond to the Tixel, thus the primary endpoint will be assessed via the percentage of study participants that demonstrated an improvement in the FWCS from baseline to the 3-month visit.
- An improvement is clinically important when FWCS ≥ 1 score.

The sample size calculation is based on the rate of subjects for which a score improvement on the FWCS at 3-month compared to baseline (success rate). The success rate is expected to be 65%.

When the sample size is 44, a two-sided 95% confidence interval for a single proportion using the large sample normal approximation will extend 0.14 from the observed proportion for an expected proportion of 0.65.

To account for possible missing data (up to 15% attrition), 51 subjects will be enrolled.

- Total N: up to 51 study participants

A study investigating the effects of RF device on the improvement of appearance of peri-orbital wrinkles (VIVACE K150409 Class II FDA approved device) utilized a FWCS cutoff as 60%, supporting this value in the present sample size computation.

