6.3. Endpoints for Analysis

6.3.1. Primary Efficacy Endpoint

The primary efficacy endpoint is the comparison of the proportion of subjects (i.e. percentage of treatment responders) with a ≥ 1 -score improvement on the FWCS at the 3- month visit, as compared to baseline as determined by at least 2 out of 3 blinded Independent Photographic Reviewers. The study design assumes a 65% success rate of subjects with treated wrinkles with a ≥ 1 -score change on the FWCS; therefore, even or greater than 65% of subjects must be rated with a ≥ 1 -score improvement 3 months after treatment. and must be statistically significantly.

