6.4.3. Handling of Missing Data

- Every effort will be made to obtain all FWCS data at month-3 evaluation from all subjects who have been enrolled to minimize missing data. However, in the event when there is missing data the following imputation methods will be used.
- Imputation using mean values: the missing FWCS value will be replaced by the average of non-missing FWCS values at month-3 in the same treatment group by the same evaluator.
- Imputation using baseline values: the missing FWCS value will be replaced by the subject's baseline FWCS value by the same evaluator.
- The MMRM model (Mixed-effect Model for Repeated Measures), which is based on MAR (missing at random) assumption will be applied to all enrolled subjects.

Sensitivity analyses will be applied for testing the effect of the imputation on the treatment effect. This will show the influence of the imputation on the study results.

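### Section 4.3 gives a success rule for the photographic rating that conflicts with the primary endpoint in 1.7.1 and 6.3.1, and its FWCS condition excludes nobody

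*Combined protocol and SAP*

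**What the plan says.** Section 4.3 describes the blinded photographic rating. Each rater views a subject's baseline and 3-month images together, without knowing which is which, and is asked to "assess which set of images represent the subject's post-treatment images". On scoring it adds: "The Raters will assign a single FWCS score per subject at each time point". It then makes a subject a success if "at least 2 out of the 3 Raters correctly identify the 3-month images and the FWCS score is ≥ 1".

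The primary endpoint is defined twice elsewhere. Section 6.3.1 counts subjects with at least a 1-score "improvement on the FWCS at the 3- month visit, as compared to baseline as determined by at least 2 out of 3" blinded photographic raters. Section 1.7.1 has the same rule, "compared to baseline as determined by at least 2 out of 3 blinded Independent Photographic Reviewers". Neither mentions identification of the images. Both require at least 65% of subjects to succeed, together with statistical significance.

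Three other places bear on the point:

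- Section 4.2 describes the FWCS as "on a scale from 1 through 9, where the lower score is considered better".
- Section 6.1 uses similar shorthand: "An improvement is clinically important when FWCS ≥ 1 score".
- Section 6.4.3 gives imputation rules for FWCS values only, for example "the missing FWCS value will be replaced by the average of non-missing FWCS values at month-3".

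**The concern.** There are three defects.

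1. **The score condition in 4.3 does no work.** No score on a 1-to-9 scale is below 1. Read literally, success is identification alone, with no improvement needed.
2. **Correcting the slip leaves two primary rules.** Section 4.3 would need improvement and identification; 1.7.1 and 6.3.1 need improvement only. Identification is not listed as a secondary endpoint in 1.7.2 or 6.3.2, so 4.3 cannot simply be read as defining a separate endpoint.
3. **The corrected rule is still ambiguous.** It does not say whether the two-of-three majority applies to the improvement as well as the identification, or whether the same two raters must meet both.

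This is the only primary efficacy endpoint, in a single-arm trial with a fixed 65% threshold. Two definitions leave room to choose after the results are known. The 65% assumption in 6.1 is stated for FWCS improvement, not for a rule that adds identification. In imputed analyses, a subject without 3-month images could have an FWCS outcome under 6.3.1 but no defined identification result under 4.3.

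**Working it through.** **The plan's own figures.** Section 6.1 gives n = 44, an expected proportion of 0.65 and a 95% half-width of 0.14. Check: 1.96 × √(0.65 × 0.35 / 44) = 0.141, which agrees. The 65% threshold on 44 subjects is 0.65 × 44 = 28.6, so 29 successes are needed (29/44 = 65.9%; 28/44 = 63.6%). One reclassified subject can decide that part of the criterion.

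**One subject under each rule, slip corrected.**

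| Rater | Identifies 3-month images | FWCS change |
|---|---|---|
| 1 | yes | falls by 1 |
| 2 | yes | none |
| 3 | no | falls by 1 |

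- Section 6.3.1: raters 1 and 3 score an improvement, so success.
- Section 4.3 as two separate majorities: raters 1 and 2 identify, raters 1 and 3 score an improvement, so success.
- Section 4.3 with the same raters meeting both: only rater 1 qualifies, so failure.

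**Size, slip corrected, same-rater reading.** Let d be the chance that a rater who scores an improvement also identifies the 3-month images. The documents give no value, so a range is shown, with identification taken as independent between raters. The chance that at least 2 of 3 raters meet a condition, each independently with probability x, is

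m(x) = 3x²(1 − x) + x³.

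The 6.3.1 success rate is fixed at 65%. Two scenarios for agreement between raters:

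- *Improvement scores independent.* m(q) = 0.65 gives q = 0.601 per rater, and the same-rater rate is m(q × d).
- *Raters fully agree on improvement.* The rate is 0.65 × m(d). For example, m(0.90) = 0.972 and 0.65 × 0.972 = 0.632.

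| d | Independent: rate | P(≥ 29 of 44) | Full agreement: rate | P(≥ 29 of 44) |
|---|---|---|---|---|
| 100% | 65.0% | 0.519 | 65.0% | 0.519 |
| 95% | 60.6% | 0.290 | 64.5% | 0.493 |
| 90% | 56.2% | 0.125 | 63.2% | 0.419 |

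The probabilities are binomial tails with n = 44. At d = 90% the expected successes are 44 × 0.562 = 24.7 to 44 × 0.632 = 27.8, against 28.6.

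These are two scenarios, not bounds. If every 6.3.1 success had exactly two improving raters, the d = 90% rate would be 0.65 × 0.90² = 0.65 × 0.81 = 52.7%.

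**Separate-majorities reading.** If identification is independent of improvement with accuracy c per rater, the rate is again 0.65 × m(c): 64.5% at c = 95% and 63.2% at c = 90%. At 90% the loss is 28.6 − 27.8 = 0.8 expected successes.

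**Literal 4.3.** Success is identification by at least 2 of 3 raters. Guessing gives m(0.5) = 50% per subject, and the chance of at least 29 of 44 is 0.024, so an inert device would seldom reach the threshold. If independent raters were 60% accurate (an assumption), m(0.6) = 64.8% and the chance is 0.508, with no FWCS change required.

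**Missing data.** The plan allows for 51 − 44 = 7 subjects without data. Section 6.4.3 can supply an FWCS value for them but no identification result.

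**The case against.** The strongest objection is that the corrected rules may hardly differ in practice. A rater sees both sets side by side, and lower scores are better. A rater who gives the true 3-month set the lower score would naturally name it as the later one. Rater 3 in the example does the opposite, which is inconsistent rating. If raters are always consistent, d = 100% and all the corrected readings give the same count. This is a fair limit on the size. However, 4.3 sets scoring and identification as two tasks and does not require consistency between them.

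Second, the literal reading is unlikely to be applied, because 1.7.1, 6.1 and 6.3.1 all point to improvement. That is accepted, and the literal figures carry little weight here.

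Third, the missing-data gap does not reach the primary analysis. Section 6.2.2 puts that on the per-protocol set, which already requires quality photographs at both visits. Baseline-value imputation also gives zero change, hence failure under either corrected rule. The gap is therefore confined to the other imputation methods, and 7 is a planning allowance rather than a ceiling.

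Fourth, 1.7.1 and 6.3.1 agree, and the outlier is one sentence among the evaluation tools. True, but that sentence states outright when a subject is a success, and nothing subordinates it to the endpoint sections.

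**Conclusion.** The concern holds. The conflict is in the text and needs no assumption: the score condition in 4.3 excludes nobody, the identification condition is absent from 1.7.1 and 6.3.1, and no section says which rule governs the sole primary endpoint. It must be fixed on that ground alone.

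The effect on results is not established. With the slip corrected, the 4.3 rate under either reading that also requires an improvement by two of three raters can only equal or fall below the 6.3.1 rate. The difference is nil if raters are consistent. It is about 2 to 9 percentage points at an assumed d of 90% in the two scenarios shown (65.0 − 63.2 = 1.8; 65.0 − 56.2 = 8.8). The tail probabilities cover only the 65% part of the success criterion; significance is required as well.

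**What to change.** Before any rater data are seen, use one responder definition in 1.7.1, 4.3 and 6.3.1, written as a change: baseline FWCS minus 3-month FWCS of at least 1.

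- **Option (a), preferred.** Keep the 6.3.1 rule as primary, delete the success sentence from 4.3, and report identification as a supportive result. This is a wording change only. Its drawback is that a rater who misidentified the images can still contribute an improvement vote.
- **Option (b).** Make identification part of the primary endpoint, in 1.7.1 and 6.3.1 as well as 4.3: *a subject is a success if the same 2 or more of the 3 raters both correctly identify the 3-month images and score baseline FWCS minus 3-month FWCS of at least 1.* No new data are needed, since raters already record both items. But 6.4.3 must then say how a subject without an identification result is counted, and the 65% assumption and the sample size of 44 must be confirmed for this stricter rule.

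Under either option, reword the clinical-importance statement in 6.1 so that it refers to a decrease in FWCS of at least 1 score.

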4.4. Global Aesthetic Improvement Scale (GAIS)

Treatment results compared to pre-treatment. The Investigator will grade the overall improvement of treatment area as indicated in Table 5 by comparing the subject's appearance in each of the follow up visits, against a photograph taken prior to procedure.

Table 5- Global Aesthetic Improvement Scale Evaluation (GAIS)

Score	1	2	3	4
Assessment	0-25% - Poor response	25-50% - Fair response	50-75% - Good response	75-100% - Excellent response

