1.3.2. Expected Possible Side Effects

In the same manner as all fractional skin treatment devices, there is risk of: Temporary swelling; Skin redness; Pain and/or burning sensation; Forming of large scabs or scabs lasting more than 15 days; Significant/thick skin peeling; Post Inflammatory Hyperpigmentation (PIH); Hypopigmentation; Sensitivity to sun exposure; Local burns; Scars, edema, erythema and watery eye for few hours after the treatment.

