6.3.2. Secondary Efficacy Endpoint

shall be assessed and quantified by the handling physician.

The following assessment methods will be applied (frontal clinical assessment or by images):

- FWCS - Fitzpatrick Wrinkle Classification Scale (at each FU visit)
- GAIS - Global Aesthetic Improvement Scale Assessment (at each FU visit)

Patients' Reported Outcomes (PROs):

- Subject Experience and Satisfaction Questionnaire (in the 2 FU visits)
- Subject Subjective Downtime Assessment (following each treatment visit)

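### The GAIS in Table 5 has no grade for worsening and none of its own for no change, so a subject who looks worse can only be graded 1 or left blank.

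*Combined protocol and SAP*

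**What the plan says.** Section 4.4 states: "The Investigator will grade the overall improvement of treatment area as indicated in Table 5". The comparison is between the subject's appearance at a follow-up visit and a photograph taken before the procedure. Table 5 then offers four grades:

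- 1: "0-25% - Poor response"
- 2: "25-50% - Fair response"
- 3: "50-75% - Good response"
- 4: "75-100% - Excellent response"

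Sections 1.7.2 and 6.3.2 list GAIS among the secondary efficacy assessments made by the treating physician. The flowchart in Table 2 schedules it at the 1-month and 3-month follow-up visits. Sections 6.2 and 6.2.2 have secondary efficacy endpoints analysed on the full analysis set and also on the per-protocol set. Section 1.5 describes a single-arm study. Among the expected side effects, Section 1.3.2 names "Post Inflammatory Hyperpigmentation (PIH); Hypopigmentation" as well as burns and scars.

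No section adds a further GAIS grade, a rule for recording worsening, or a rule for values that fall on a band edge. Section 6 gives no summary statistic or responder cut for GAIS.

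**The concern.** A scale meant to compare appearance after treatment with appearance before it should be able to record three directions: better, the same and worse. Table 5 records degrees of better only. The protocol itself lists effects that could leave the treated area looking worse, so the missing direction is foreseeable.

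The design makes this matter more than it otherwise would. There is no control group in which the same floor would operate and offset it. The grader is the investigator, who compares the subject with a pre-procedure photograph and so knows which appearance is post-treatment. What is at stake is how a named secondary endpoint is read. Once sites have recorded only grades 1 to 4, subjects who were worse, unchanged or slightly better cannot be separated from the GAIS data.

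**Working it through.** The plan attaches no number to GAIS, so there is no GAIS figure to reproduce. The only sample-size calculation, in Section 6.1, concerns the FWCS success rate. Its half-width is 1.96 × √(0.65 × 0.35 / 44) = 0.141, which agrees with the stated 0.14. GAIS does not enter it.

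**Step 1: place values in the bands.** The inputs are the four bands of Table 5, taken as printed with both ends included.

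| Change in appearance | Grades that contain it |
|---|---|
| −10% (worse) | none |
| 0% (no change) | 1 |
| 10% | 1 |
| 25% | 1 and 2 |
| 50% | 2 and 3 |
| 75% | 3 and 4 |
| 100% | 4 |

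The value −10% stands for any worsening.

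**Step 2: what happens to a worsened subject.** No band contains a negative value and no instruction covers the case. Two outcomes are possible.

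- *Graded 1.* The subject takes the same score as someone unchanged or up to 25% better. Any scale with a lower grade would have scored the subject below 1, so the recorded mean is at least as high and the distribution is shifted up or left the same.
- *Left blank.* The imputation rules in Section 6.4.3 are written for missing FWCS values and give none for GAIS. If the subject drops out of the summary, the person removed belongs below every graded subject. The mean of those who remain is then higher than the mean with that person included at a lower grade.

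Both routes point the same way.

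**Step 3: what happens to an unchanged subject.** Zero lies inside grade 1, so a valid grade exists. What is lost is the distinction from a small improvement.

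**Step 4: the band edges.** Values of 25, 50 and 75% each belong to two grades. A rater may resolve the tie upward or downward, so this adds inconsistency between raters but has no built-in direction.

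**Step 5: how many subjects.** The documents give no expected rate of worsening or of no change on GAIS, and none for values at a band edge. The number affected cannot be calculated.

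**The case against.** The strongest reply is that little depends on GAIS. It is one of several secondary assessments, and no success threshold, hypothesis test or sample size rests on it. The primary endpoint uses three blinded raters on the FWCS. This stands, and it limits the weight of the point.

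A reader might infer that harm would go unseen. The documents do not support that. Sections 5.1 and 5.2 have adverse events elicited at each visit and recorded whatever their cause, from first exposure to the last follow-up. Section 6.4.1 summarises them by type, onset, duration, severity and relationship. Table 2 schedules a facial skin examination at every clinic visit. Worsening of wrinkles can also show on the investigator's 1-to-9 FWCS at the same two follow-up visits. That cover is partial: the FWCS descriptors concern wrinkles, elastosis, skin folds and dyschromia, and do not mention scars or burns. A subject with fewer wrinkles and a new scar could improve on FWCS, and GAIS could not record a worse overall appearance.

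A reader might also want to size the effect as a change in the proportion graded good or better. The plan defines no such cut. If one were used, worsened, unchanged and slightly improved subjects would all fall below it, so the floor would not move it as long as those subjects stay in the denominator. Of the three shared edges, only 50% could.

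Finally, grade 1 carries the label of a poor response, so a worsened subject placed there is not presented as a success. That is fair, but the grade still states 0 to 25% improvement.

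**Conclusion.** The point holds as a gap in the measuring scale of a secondary endpoint, and it is worth correcting because the correction is cheap. Table 5 has no place for worsening and merges no change with improvement up to 25%. In a single-arm study this can only favour the device on a mean score or grade distribution. The size is unknown and is zero if no subject worsens and none is unchanged.

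That a worsened subject would be graded 1 or left blank is an inference from the absence of any other option; the documents do not state it. The direction of the effect assumes the comparison is with a scale that has lower grades and, for blanks, that missing GAIS scores are not imputed.

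It would go too far to say that the scale cannot record zero improvement, since 0% lies in grade 1, or that the shared edges bias the result upward, since ties can go either way. The edges alone would be a matter of missing detail. The primary endpoint, the sample size and the capture of adverse events are unaffected.

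**What to change.** Add two grades to Table 5 and to the corresponding CRF field: 'no change' and 'worse'. Report each separately at both follow-up visits. In the same edit, make the improvement bands exclusive: >0 to <25%, 25 to <50%, 50 to <75%, and 75 to 100%. This sends edge values to the higher band; what matters is that one rule is written down before grading.

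The cost is one table and one CRF field, with no added visit, procedure or subject. The downside is a slight departure from the four-grade form now in the protocol. Presenting a second summary with 'no change' and 'worse' merged into grade 1 recovers that form. The reverse is not possible: the distinction cannot be rebuilt from data recorded only as 1 to 4.
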